## 5.4.3 Clinical Laboratory Variables

Hematology, biochemistry and urinalysis assessments will be taken at visit 1/week -2 (screening), and visit 5/week 12 (EoT).

All clinical laboratory assessments will be performed at a local laboratory. Urine pregnancy tests (female subjects of childbearing potential only) will be performed according to the clinical site's preferred method at visit 1/week -2 (screening) and visit 5/week 12 (EoT) except for cases in which the possibility of pregnancy was clearly ruled out by hysterectomy, bilateral oophorectomy or the passage of 2 or more years after last menstruation.

A blood sample will be collected for serology tests (HAV antibodies [IgM], HBc antibodies, HBsAg, HCV antibodies, syphilis and antibodies to HIV types 1 and 2) at screening only.

Additional hematology, biochemistry and urinalysis (UA dipstick) tests may be performed at visit 1/week -2 (screening) and visit 5/week 12 (EoT). If any of the clinical laboratory tests results are outside the normal range at any scheduled time point during the study, the investigator may decide to repeat the test(s) on new samples. The clinical relevance of the abnormal results will be documented. Clinically relevant changes will be recorded as AEs (see Section 7.3 of protocol).

The laboratory parameters that will be assessed during the conduct of the study are listed in Table 4.

Hematology	Biochemistry	Urinalysis	Serology*
Hematocrit	Albumin	Leukocyte esterase	HAV antibodies
Hemoglobin	Alanine aminotransferase	Nitrites	(IgM)
Mean corpuscular volume	Alkaline phosphatase	pH	HBsAg
Mean corpuscular	Aspartate aminotransferase	Protein	HBc antibodies
hemoglobin	Bicarbonate	Red blood cells	HCV antibodies
Mean corpuscular	Blood urea nitrogen	Human chorionic	HIV antibodies
hemoglobin concentration	Calcium	gonadotropin (female	types 1 and 2
Platelets	Chloride	subjects only)	Syphilis
Red blood cell count	Corrected serum calcium		
White blood cell count	Creatinine		
White blood cell count	Creatinine kinase		
differential	Glucose		
	Lactate dehydrogenase		
	Magnesium		
	Phosphate		
	Potassium		
	Sodium		
	Total bilirubin (total and		
	direct)		
	Total protein		

Table 4Laboratory Assessments

\* Serology parameters will be only collected at screening.

The value of each hematology and biochemistry parameter will be compared to its normal range and classified as High, Low or Normal. Urinalysis parameters will be similarly classified as either Normal or Abnormal.

When calculating changes or shifts in a result from baseline, the value from visit 1 will be used as baseline. If the visit 1 value is missing, the latest pre-baseline value will be used (i.e., from Visit 1 or any unscheduled visit conducted between Visit 1 and Visit 2).

### 5.4.4 Physical Examination

Physical examinations will be performed at visit 1/week -2 (screening) and visit 5/week 12 (EoT) and whenever there is a medical indication and will include assessments of the main body systems.

The physical examination will be performed per clinic standards and clinically significant findings at screening will be recorded as part of the subject's medical history. Any abnormal finding observed at screening must be assessed and documented as not clinically significant if a subject is to be enrolled in the study.

After IP administration, new clinically significant findings or a worsening of an ongoing clinically significant abnormal condition will be recorded as an AE [see Section 7.3 of protocol: Adverse Events and Other Safety Aspects].

### 5.4.5 12 Lead ECGs

A 12-lead ECG will be performed as single measurement at visit 1/screening and visit 5/week 12 (EoT). ECG traces will be evaluated by the investigator who will give an overall interpretation and may leave a qualifying comment in the eCRF. The overall interpretation will be recorded as:

- Normal, or
- Abnormal not clinically significant, or
- Abnormal clinically significant

As well as the overall interpretation, the following ECG variables will be supplied by the local laboratory: PR Interval (msec), RR Interval (msec), QRS Duration (msec), QT interval (msec) and Heart Rate (HR) (beats/min).

### 5.4.6 Post Void Residual Volume

PVR volume will be assessed by ultrasonography at visit 1/week -2 (screening) and visit 5/week 12 (EoT). For each subject, the same method should be used throughout the study. The bladder should only be emptied when it was initially filled with preferably > 50% of the bladder capacity for age. Every attempt should be made to measure PVR within a minute of voiding. A PVR of  $\leq$  100 mL is sufficient and the assessment does not have to be repeated. If the PVR is > 100 mL, the PVR assessment should be repeated (filled with preferably > 50% of the bladder capacity for age). If the subject is unable to complete a second measurement, it is up to the investigator to judge whether it can be skipped (and write the reason in the eCRF). The lowest PVR volume result measured should be used to evaluate the exclusion criterion. In case the lowest PVR volume measured is  $\geq$  100 mL at visit 1/week -2 (screening), the subject should be excluded from the study.

## 5.5 Other Endpoints

### 5.5.1 Exposure to Study Drug

The duration of exposure to each dose of study drug (Mirabegron 25 mg and Mirabegron 50 mg) by visit and for the whole period will be calculated using the following information :

- Overall start date and stop date of the study medication. The first dose of study drug is to be administered on Day 1, the day on visit 2/week 0 [baseline]. Treatment will be administered once daily orally after meal during a 12-week, open-label treatment period.
- Start date and new dose of study drug at each titration step. At visit 3/week 4 or visit 4/week 8 the dose may be up-titrated (from 25 to 50 mg according to investigators' discretion), or may remain the same. The study does not allow dose reduction from 50 mg to 25 mg as the former is considered a safe and effective recommended dose.

- Start date and new dose of study drug after each unscheduled dose change.
- At any time during the treatment period, the subject may have an unscheduled dose interruption. At each unscheduled change in dose, the (new) dose, start date and reason are recorded.

In all cases where there is a dose change, either because of dose titration or an unscheduled dose interruption, the first and the last dose of the medication at the old level will be collected at the CRF. In this way, the subject's dosing history can be reduced to a series of unbroken intervals within each of which, the dose level is constant. From these, the subject's exposure at each dose can be calculated.

To illustrate, consider a subject with the following dose information on the eCRF:

- The dates of the very first and very last dose of the study medication given at  $D_1=1^{st}$  July 2020,  $D_{last}=23^{rd}$  September 2020.
- Up-titration to 50 mg at Visit 3. The first dose at the new level is given at  $D_2=29^{th}$  July 2020.
- Study drug interrupted at an unscheduled visit. The date of last dose is given at D3=1st August 2020.
- Study drug re-started at an unscheduled visit at  $D_4=5^{th}$  August 2020.
- Remains at 50 mg till Visit 5 (Dlast=23rd September 2020).

From these dates we calculate the following:

- The duration of exposure to the treatment can be calculated as  $E_{TOT}=D_{last}-D_1+1-(D_4-D_3-1)$ =82 days.
- Between Visits 2 and 3, the subject is on 25 mg. If the last dose at 25 mg collected in CRF is given on D2-1, the day before the subject has the first dose at the new level (50 mg), then the exposure at 25 mg between Visits 2 and 3 is, therefore, (D2-1)-D1+1=28 days
- Between Visits 3 and 5, the study drug is temporarily suspended and then restarted. The subject will be considered to be exposed to the 50 mg dose from D2 until D3, i.e. D3-D2+1=4 days.
- For the calculation of the exposure, suspension of the study drug is accounted. The dose will be considered interrupted between  $D_3+1$  to  $D_4-1$ , i.e.,  $(D_4-1) (D_3+1) + 1 = 3$  days.
- The study drug is at 50 mg from D4 to Dlast, the date of the last dose on Visit 5, i.e., (Dlast-D4+1)=50 days.
- The total exposure at 50 mg is  $E_{50}$ =54 days, and at 25 mg total exposure is  $E_{25}$ =28 days.

### 5.5.2 Compliance to Study Drug

Compliance will be calculated according to the number of tablets of study medication dispensed, the number of tablets used and the duration of exposure between the applicable visits and overall.

The total number of tablets used between Visits i and j (i=2 [baseline], 3, 4, and j=i+1) is calculated as:

Nused = Total number of tablets dispensed at Visit i - Total number of tablets returned at Visit j

If some tablets (or part of kits) of IP are lost by the subject or returned later than expected, investigator will document the reason and IP compliance will be calculated based on actual tablets taken by subjects and IP accountability log.

When a strip with study drug is not returned/not reconciled, then for the calculations it is assumed that all tablets were taken from that strip.

The amount of expected study drug intake depends on the number of days of study drug treatment and the number of prescribed daily tablets. Since subjects are supposed to take 1 tablet per day, the total number of expected tablets to be used between Visits i and j (i=2 {baseline], 3, 4, and j=i+1) is calculated as described below.

For the compliance calculations it is assumed that on the visit day at Visit 3 (week 4), Visit 4 (week 8) and Visit 5 (week 12), the tablet is taken at home before going to the clinic. For the baseline visit (Visit 2) the subject takes the tablet at the clinic (Day 1). For the period from:

- Baseline to Week 4 the expected number of tablets taken is equal to: Date of drug returned at Week 4 Date of drug dispensed at Baseline visit + 1.
- Week 4 to Week 8 and from Week 8 to Week 12 the expected number of tablets taken is equal to: Date of drug returned Week (i+4) Date of drug dispensed (Week i), where i=4 or 8.

Between Visits i and j the compliance to study medication will be calculated as follows:

Compliance = 
$$(N_{used} / N_{prescribed}) \times 100\%$$
.

For the whole study period, the total amount of study drug used (TOTNused) is equal to the sum of the values of  $N_{used}$  at each applicable visit. Similarly, the total amount of study drug prescribed (TOTNprescribed) is equal to the sum of the values of  $N_{prescribed}$  at each applicable visit. Using these total values, the subject's compliance over the whole study period will be calculated as 100% x (TOTNused/TOTNprescribed).

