#### 6.3.2 Treatment Compliance

Total compliance with the dosing schedule will be examined for subjects in the SAF whose total study drug count and first and last days of treatment are known.

Percent total compliance will be summarized in two ways for the SAF:

- Descriptive statistics will be presented by treatment group.
- Percent compliance will be categorized according to the following categories by treatment group:
  - less than 70%
  - $\circ~$  at least 70%, less than 80%
  - at least 80%, less than 120%
  - at least 120%

• Unknown.

Treatment compliance details, including all data relevant to the calculation, will be listed for each subject by study visit and total for all randomized subjects.

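### The compliance formula counts expected tablets up to the drug-return date, so days after the last dose and recorded interruptions are charged as missed doses

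*SAP*

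**What the plan says.** SAP 5.5.2 states the principle for the denominator: "The amount of expected study drug intake depends on the number of days of study drug treatment" and on the daily number of tablets, which is one. It also names the duration of exposure as an input to compliance. SAP 6.3.2 restricts total compliance to subjects in the safety analysis set "whose total study drug count and first and last days of treatment are known".

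The formulas in 5.5.2 use other dates. From baseline to Week 4 the expected number is "Date of drug returned at Week 4 Date of drug dispensed at Baseline visit + 1". For the two later intervals it is "Date of drug returned Week (i+4) Date of drug dispensed (Week i), where i=4 or 8". Both are read here as the difference between two dates. Neither contains a last-dose date or a term for interruptions.

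The numerator is "Total number of tablets dispensed at Visit i - Total number of tablets returned at Visit j". Two rules cover tablets that do not come back as planned. If tablets or part of a kit are lost or returned late, the reason is documented and "IP compliance will be calculated based on actual tablets taken by subjects and IP accountability log". Then, as a separate rule: "When a strip with study drug is not returned/not reconciled, then for the calculations it is assumed that" every tablet on that strip was taken. The section does not say which rule goes first.

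SAP 6.3.2 reports total compliance with descriptive statistics and in five categories: below 70%, 70% to below 80%, 80% to below 120%, 120% or more, and Unknown.

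**The concern.** The formula does not carry out the principle stated in the same section. Tablets are not due after permanent discontinuation or during a recorded interruption, yet the formula expects one on each such day until drug is returned. A subject who took every tablet while on treatment can then be tabulated as a poor complier.

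A delay between last dose and return is possible under the protocol. Section 8.1 encourages subjects who stop treatment to complete all scheduled visits, and section 8.2 keeps them in the study. The Schedule of Assessments collects drug at scheduled visits and asks early withdrawals for an end-of-treatment visit, but sets no limit on the days from last dose to that visit.

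The strip rule acts on the numerator and in the other direction: it can raise the count for a subject whose true intake is unknown. At stake is whether the compliance table describes adherence correctly.

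**Working it through.** **Inputs.** Dose dates: worked example in SAP 5.5.1. Formulas: SAP 5.5.2. Strip size of 10 tablets: protocol 6.1, Table 3. Visits are put on Days 29, 57 and 85. Days 29 and 85 match the example in SAP 5.5.1 (1 July to 29 July and to 23 September 2020); Day 57 follows from 28-day spacing. Strips dispensed per visit are not stated; 3 and 4 are assumed.

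**Step 1: reproduce the SAP's exposure example.** First to last dose is 85 days. The interruption between 1 and 5 August is 3 days. Exposure = 85 - 3 = 82 days, made up of 28 days at 25 mg and 4 + 50 = 54 days at 50 mg. All three figures match the SAP.

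**Step 2: apply the compliance formula to the same subject.** Suppose the subject took every tablet due and returned drug at Visit 5. Expected tablets = 29 + 28 + 28 = 85. Compliance = 82/85 = 96.5%. On days of treatment it is 82/82 = 100%.

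**Step 3: permanent stop, drug returned at the next scheduled visit.** With every tablet taken to last-dose day L and drug returned on day R, expected tablets add up to R and total compliance = L/R. Compliance while on treatment is 100% in every row.

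| Last dose (L) | Return (R) | L/R |
|---|---|---|
| 10 | 29 | 34.5% |
| 20 | 29 | 69.0% |
| 21 | 29 | 72.4% |
| 39 | 57 | 68.4% |
| 43 | 57 | 75.4% |
| 59 | 85 | 69.4% |
| 70 | 85 | 82.4% |

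The 70% limit is crossed at L = 0.70 x R, that is 20.3, 39.9 and 59.5. Stops on Days 1-20, 30-39 and 58-59 therefore fall below 70%.

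**Step 4: earlier return.** Suppose drug comes back g days after the last dose, at a visit whose date takes the place of the scheduled return date. Compliance = L/(L + g), which is below 70% when L < (7/3) x g.

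| Lag g (days) | Below 70% for stops up to |
|---|---|
| 0 | none (always 100%) |
| 3 | Day 6 |
| 7 | Day 16 |
| 14 | Day 32 |

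**Step 5: the strip rule read alone.** A subject takes one tablet and returns nothing at any visit. True intake is 1/85 = 1.2%. With 3 strips per visit the rule gives (3 x 30)/85 = 90/85 = 105.9%, in the 80% to below 120% category. With 4 strips it gives 120/85 = 141.2%, in the 120% or more category.

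**The case against.** The strongest reply is that counting days off treatment is a matter of definition. If the denominator stops at the last dose, a subject who simply quits on Day 10 scores 100%, which hides a different kind of non-adherence. That cost is real. But the SAP has already chosen: it ties expected intake to treatment days, and its formula departs from that choice. Early stopping also stays visible in the duration-of-exposure summary (SAP 6.3.1) and in the discontinuation table by reason (SAP 6.2.1).

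A second reply is that 34.5% is an extreme case needing a 19-day gap between last dose and return. This stands in part. A prompt end-of-treatment visit removes most of the effect, and a short interruption costs little, as the 96.5% shows. No limit on the gap is given, however.

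Third, the strip rule can be read as a fallback once the log has failed, and 6.3.2 already asks for a known drug count. This is a fair reading, so the defect is an unstated precedence. The SAP also does not say whether an unreconciled strip makes the count unknown.

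Four stronger conclusions are tempting, and the documents do not support them:

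- That every unreturned strip counts as taken, so that people who took nothing appear fully compliant. The log rule precedes the strip rule, and the safety analysis set requires at least one dose. A figure near 100% also needs 3 strips per visit; with 4 the subject stands out at 120% or more.
- That the errors cannot be separated afterwards. SAP 6.3.2 lists all inputs to the calculation by subject and visit.
- That the planned 25% drop-out, about 42 of 166 subjects in the 50 mg arm (0.25 x 166 = 41.5), measures how many are affected. It is a ceiling: subjects who stop at a visit have no gap, and those who never return drug supply no return date.
- That the efficacy claim rests on this table. The analysis sets (SAP 4), the primary repeated-measures model (SAP 6.4.1.1) and the protocol deviation criteria (SAP 6.2.2) do not use compliance.

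**Conclusion.** The point holds for the denominator. As written, it contradicts the treatment-days principle of its own section and can put subjects who took every tablet until they stopped into the lowest compliance category. The size depends on the gap between last dose and drug return: none at 0 days; below 70% only for stops by Day 16 at 7 days; and below 70% for stops on about Days 1-20, 30-39 and 58-59 if drug comes back at the next scheduled visit. This assumes visits on Days 29, 57 and 85 and full intake until stopping. The documents do not allow an estimate of how many subjects this would touch.

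The strip rule is a secondary point: two rules without an order. Its figures of about 106% and 141% rest on the assumed 3 or 4 strips per visit and on the rule being applied without the log.

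The consequence is confined to a descriptive table and its listings. The primary result is unaffected. The change is still worth making, because it brings a reported result into line with the SAP's own principle at little cost.

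**What to change.** In SAP 5.5.2:

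1. Define the prescribed number of tablets in each interval as the days from first to last dose in that interval, minus recorded interruption days, using the dose dates already collected for SAP 5.5.1. The Day 10 subject then scores 10/10 and the exposure-example subject 82/82.
2. Add a note that the table shows compliance while on treatment and is to be read beside the exposure and discontinuation tables.
3. State that the accountability-log count applies first. If a strip still cannot be reconciled, place the subject in the existing Unknown category of 6.3.2 and show how many there are.

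The interval definition also needs a consistent account of the visit-day tablet. SAP 5.5.2 assumes it is taken at home at Visits 3 to 5, while protocol 5.3 has visit-day dosing in the clinic. The two passages must be reconciled.

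The cost is SAP wording and programming; no new data are needed. Early stoppers will show on-treatment compliance only. Some subjects will move to Unknown and may be poorer compliers than the rest. Because SAP 6.1 bases percentages on subjects without missing data, their number must appear in the table.

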# **6 STATISTICAL METHODOLOGY**

## 6.1 General Considerations

Continuous data will be summarized descriptively including the number of subjects (n), mean, standard error of the mean (SEM) (efficacy data), standard deviation (SD), median, minimum and maximum. Categorical data will be summarized by frequencies and percentages. Percentages by categories will be based on the number of subjects with no missing data, i.e., the percentages for the non-missing categories will add up to 100%.

All statistical comparisons will be conducted using 2-sided tests at the 5% significance level unless stated otherwise. All null hypotheses will be of no treatment difference, all alternative hypotheses will be two-sided, unless specifically stated otherwise.

All data summarization and analyses will be performed using SAS® Version 9.4 or higher on Linux. Specifications for table, figures, and data listing formats can be found in the TLF specifications.

# 6.2 Study Population

All study population summaries will be presented showing two treatment groups as:

- Mirabegron 25 mg (Total)
- Mirabegron 50 mg (As-Randomized)
- Total Mirabegron, i.e., the sum of the Mirabegron 25 mg (Total) and of Mirabegron 50 mg (As-Randomized)

#### 6.2.1 Disposition of Subjects

The following subject data will be presented by treatment arm, unless stated otherwise:

- Number of subjects with informed consent, discontinued before randomization, randomized (total only) (All Enrolled Set)
- Number and percentage of subjects randomized in each analysis set, by treatment group and total (All Randomized Set)
- Number and percentage of subjects completed and discontinued the screening (including COVID-19 reasons), by primary reason for study discontinuation (total only) (All Enrolled Set)
- Number and percentage of subjects completed and discontinued treatment, by primary reason for treatment discontinuation (including COVID-19 reasons), and by treatment group and total (All Randomized Set)
- Number and percentage of subjects who completed the Week 0, Week 4, Week 8 and Week 12 visit by treatment group and total (All Randomized Set)
- Number and percentage of subjects completed and discontinued the follow-up period, by primary reason for post-study period discontinuation (including COVID-19 reasons), and by treatment group and total (All Randomized Set)
- Number and percentages of subjects screened and randomized to each treatment group under each protocol version (All Subjects With Informed Consent).

A listing of inclusion and exclusion criteria, listing of first and last evaluations as well as a listing of subjects who were excluded from at least 1 analysis set will be provided for the All Enrolled Set.

### 6.2.2 **Protocol Deviations**

The number and percentage of subjects with the following protocol deviation criteria will be summarized for each criterion and total by treatment group and total as well as by investigative site. Subjects deviating from a criterion more than once will be counted once for the corresponding criterion.

The unique identifiers will be as follows:

PD1 - Entered into the study even though they did not satisfy entry criteria

- PD2 Developed withdrawal criteria during the study and was not withdrawn
- PD3 Received wrong treatment or incorrect dose
- PD4 Received excluded concomitant treatment
- PD5 Issues related to missing or invalid baseline Diary/OABSS

#### 6.2.3 Demographic and Other Baseline Characteristics

Demographic and other baseline characteristics will be summarized by descriptive statistics. Summaries will be presented by treatment group and total.

For the SAF and FAS, descriptive statistics for age will be presented as well as frequency tabulations for sex, ethnicity, race ('Chinese' or 'Other') and prior OAB treatment (Yes/No).

Medical history is coded in MedDRA, and will be summarized by System Organ Class (SOC) and Preferred Term (PT) as well as by PT alone, by treatment group for the SAF.

Demographic data and other baseline characteristics (including medical history) will be provided in listing format by site and subject for the All Randomized Set.

